### **10.2. Withdrawal From the Study**

Because the primary endpoint of this study is time to all-cause discontinuation, investigators should ensure that appropriate withdrawal criteria have been met when withdrawing a subject from the study, especially when subjects are withdrawn due to lack of efficacy. The investigator should complete a detailed summary of the discontinuation, including the reasons for withdrawal and time of the withdrawal, in the CRF and in the source document. If the withdrawal results from an AE, the clinical course of the AE and the outcome (recovered, resolving, or ongoing) of the AE should be documented.

A subject will be automatically withdrawn from the study for any of the following reasons:

- Lost to follow-up
- Withdrawal of consent
- Death
- Noncompliance with study drug administration (ie, missing either 4 or more consecutive doses of study medication or a total of 20 or more doses during the 6-month period)
- Investigator's impression of noncompliance with background antidepressant therapy
- Discontinuation of study treatment for any reason. A subject's study treatment will be automatically discontinued if:
  - The investigator or sponsor believes that for safety reasons or tolerability reasons (eg, AE) it is in the best interest of the subject to discontinue study treatment
  - The subject becomes pregnant
  - The subject shows signals of acute suicidal ideation with a clear plan at any time during the study; the subject should be referred to appropriate medical/psychiatric care

- AST and/or ALT exceeds 5 x Upper Limit of Normal (ULN) (confirmed by repeat testing)
- AST and/or ALT exceeds 3 x ULN and total bilirubin exceeds 1.5 x ULN (confirmed by repeat testing).

If a subject withdraws from the study before the end of the double-blind phase (ie, Day 168), end-of-study/follow-up assessment should be obtained.

If a subject is lost to follow-up, every reasonable effort must be made by the study-site personnel to contact the subject and determine the reason for discontinuation/withdrawal. The measures taken to follow-up must be documented. If a subject leaves the study due to withdrawal of consent, the investigator will make sure that there is not a reason for the withdrawal of consent such as lack of efficacy or poor tolerance (ie, due to an AE).

Study drug assigned to the withdrawn subject may not be assigned to another subject. Subjects who withdraw will not be replaced.

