1.4. Sample Size Justification

The primary purpose of the study is to investigate potential differentiating features between JNJ-42847922 and quetiapine XR. Although the sample size was not chosen based on a specific

set of endpoints, for evaluating the time to discontinuation of study drug in the JNJ-42847922 group versus the quetiapine XR group, a one-sided log-rank test with an overall sample size of 100 subjects (50 in the JNJ-42847922 group and 50 in the quetiapine XR group) provides approximately 92% power at a 1-sided 0.10 significance level to detect a hazard ratio of 0.415, assuming the proportion of subjects who discontinue from study drug in the quetiapine XR group is 50%. The planned sample size of the study is consistent with the nature of a Phase 2 exploratory study.

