5.1. Analysis Specifications

5.1.1. Level of Significance

The primary efficacy endpoint will be evaluated at a two-sided significance level of 0.20. For all other efficacy endpoints, no multiplicity adjustment will be done and point estimates and confidence intervals will be presented.

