5.3.1.2. Analysis Methods

Descriptive statistics of the actual values on Baseline, Week 2, Week 4, Week 6, Week 12, Week 18, Week 24, and at follow-up and the change from baseline to each postbaseline time point will be presented for MADRS total score by treatment group. A frequency distribution of the MADRS individual item scores at each time point will be provided by treatment group.

MMRM

A mixed model for repeated measures (MMRM) analysis of the observed data from the JNJ-42847922 and quetiapine XR groups will be used to adjust for important covariates. The MMRM will include time (scheduled Week), treatment (JNJ-42847922 and quetiapine XR), baseline insomnia status (present/absent), and treatment-by-time interaction as factors and baseline MADRS total score as a covariate. Data from the follow-up phase will not be used. An unstructured variance-covariance matrix will be used for observations clustered by subject. In case of convergence problems, alternative variance-covariance structures will be tried in the following order, with the first structure that converges being used in the analysis: heterogeneous Toeplitz, standard Toeplitz, and AR(1) with separate subject random effect. Subjects in the full analysis set who do not have complete data will still contribute to the estimates at each time point, but will have less weight in the analysis than those subjects with complete data. The

Kenward-Roger method will be used for approximating the denominator degrees of freedom. Based on the MMRM, the comparison between JNJ-42847922 and quetiapine XR will be performed using the appropriate contrasts directly from the MMRM analysis, using estimates at each postbaseline time point. A 80% confidence interval (CI) for the difference in least-squares (LS) means will be calculated based on the contrast test statistic.

As a secondary analysis, age and gender will be added to the MMRM model.

Means and mean changes from baseline (+/- SE) in MADRS will be presented graphically over time. Least squares mean changes from baseline (+/- SE) in MADRS will be presented graphically over time.

ANCOVA

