5.3.4.2. Analysis Methods

Descriptive statistics of the actual values on Baseline, Week 6, Week 12, Week 18, Week 24, and at follow-up and the change from baseline to each postbaseline time point will be presented for HAM-A total score, and HAM-A somatic and psychic factor scores by treatment group.

The change from baseline in HAM-A total score will be analyzed using the same MMRM as described in Section 5.3.1.2 for MADRS total score, with the continuous covariate “baseline MADRS total score” changed to “baseline HAM-A total score”.

As a sensitivity analysis, the change in HAM-A total score from baseline to each postbaseline time point will be analyzed using an ANCOVA model, using LOCF data. The derivation of the LOCF values is described in Section 5.3.1.2. The ANCOVA model will include factors for treatment, baseline insomnia status (present/absent), and baseline HAM-A total score as a continuous covariate. A 80% CI for the difference in LS Means will be calculated based on the contrast test statistic.

In addition, a frequency distribution over time of the HAM-A total score categories and HAM-A individual item scores at each time point will be provided by treatment group.

The shift in HAM-A total score categories (normal, mild, mild to moderate, moderate to severe, severe) from baseline to each time point will be presented by treatment group.

The correlations between HAM-A total score and MADRS total score will be evaluated using Pearson and Spearman correlation coefficients at each time point. These correlations will look at the correlations of the change from baseline. Scatter plots will also be presented.

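### The MMRM in SAP 5.3.1.2 fits one baseline-score slope for all visits; if that slope changes over time and baseline-related dropout leaves the arms unbalanced, the Week 24 difference carries a small avoidable bias

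*SAP*

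**What the plan says.** SAP 5.3.1.2 models change in MADRS total score with time, treatment, "baseline insomnia status (present/absent), and treatment-by-time interaction as factors and baseline MADRS total score as a covariate". Treatment may act differently at each visit, but baseline score enters once, with one coefficient. The covariance is unstructured, with Kenward-Roger degrees of freedom and an 80% confidence interval for the difference at each visit. The only planned variant of the mean model adds age and gender.

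SAP 5.3.4.2 analyses HAM-A "using the same MMRM as described in Section 5.3.1.2 for MADRS total score", substituting the HAM-A baseline. QLDS (5.3.7.2), PROMIS-SD (5.3.8.2), PROMIS-SRI (5.3.9.2), SMDDS (5.3.10.2), SDMT (5.3.11.2), TMT-Part B (5.3.12.2), MADRS-6 (5.3.14.2), the CSD-M parameters (5.4.1.2) and MADRS-WOSI (5.4.2.2) do the same. CGI-S and PGI-S use ANCOVA on ranks (5.3.5.2, 5.3.6.2), and HVLT-R is only described (5.3.13.2).

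On dropout, SAP 1.4 claims "approximately 92% power at a 1-sided 0.10 significance level to detect a hazard ratio of 0.415". It takes half of the quetiapine XR arm to stop study drug, and it plans for 50 subjects per arm. Protocol 10.2 lists "Discontinuation of study treatment for any reason" among the grounds for automatic withdrawal from the study, so later scores will be missing.

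**The concern.** In a model of change from baseline, the coefficient on baseline need not be the same at Week 2 and Week 24. If it changes, a single coefficient is a compromise, and it is drawn towards the early visits, which are more complete and, under the inputs assumed below, less variable. It is then wrong at Week 24.

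Randomisation makes that harmless while the arms have the same mean baseline. It stops protecting the comparison once the subjects still observed at Week 24 differ in baseline between arms, which can happen when the arms lose different numbers of subjects and loss is related to baseline score.

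Dropout that depends on an observed baseline is the simplest kind of missingness that a likelihood-based repeated-measures model should handle, and the stated mean model may not handle it. For QLDS, PROMIS-SD, PROMIS-SRI, SMDDS, SDMT, TMT-Part B and MADRS-WOSI, the MMRM is the only modelled treatment comparison.

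**Working it through.** **1. The plan's own figure, and the dropout it implies.** Inputs from SAP 1.4: 50 per arm, 50% discontinuation on quetiapine XR, hazard ratio 0.415, one-sided alpha 0.10.

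- Discontinuation on JNJ-42847922 (derived, not stated): 1 − 0.5^0.415 = 0.250.
- Expected events: 50 × 0.50 + 50 × 0.25 = 37.5.
- Power (Schoenfeld): Φ(√37.5 / 2 × |ln 0.415| − 1.2816) = Φ(2.693 − 1.282) = 0.921.

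This reproduces the stated 92%. The two-sided 0.20 level in SAP 5.1.1 gives the same value. The plan therefore expects about 50% against 25% of subjects without Week 24 data.

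**2. Assumed inputs.** The documents give no MADRS SD, no slope by visit and no link between baseline and dropout. The main simulation assumed:

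- baseline SD 5;
- raw-score slope on baseline falling from 0.8 at Week 2 to 0.35 at Week 24, so the slope for change runs from −0.20 to −0.65;
- residual SD rising from 6 to 10, with correlation 0.9 between adjacent visits;
- dropout hazard × 1.65 per baseline SD.

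A maximum-likelihood MMRM with unstructured covariance was fitted over six visits, with 60,000 per arm and three replicates.

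**3. Week 24 error** (JNJ-42847922 minus quetiapine XR, MADRS points; negative favours JNJ-42847922):

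| Setting | One slope | With baseline-by-time | Baseline difference in completers |
|---|---|---|---|
| A. Constant slope, baseline-dependent dropout, 50% v 25% | −0.03 | −0.03 | +0.89 |
| B. Changing slope, dropout unrelated to baseline | −0.04 | −0.04 | 0.00 |
| C. Changing slope, baseline-dependent dropout, 37.5% in both arms | −0.02 | −0.02 | 0.00 |
| D. Changing slope, baseline-dependent dropout, 50% v 25% | −0.33 | −0.03 | +0.89 |
| D, adjacent-visit correlation 0.7 | −0.34 | −0.04 | +0.89 |
| D, baseline SD 7 | −0.44 | −0.03 | +1.25 |
| D, hazard × 2.7 per SD | −0.53 | −0.03 | +1.36 |
| F. As D, dependence in the quetiapine XR arm only | −0.54 | −0.03 | +1.57 |
| G. As D, opposite dependence by arm | −0.75 | −0.02 | +2.27 |

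The −0.02 to −0.04 that remains with the added term is simulation noise. More extreme slopes (raw 1 falling to 0) gave −0.66 with the dependence of D, and −2.85 with strong opposite dependence in the two arms.

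**4. Why D gives this size.** The fitted common slope in D was −0.20, which is the Week 2 value, against a true −0.65 at Week 24. The slope error is −0.45 and the completers differ by 0.89 in baseline, so a crude bound is −0.45 × 0.89 = −0.40. The simulated bias net of noise is −0.33 + 0.03 = −0.30, smaller because the model also borrows from earlier visits.

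**5. A second simulation** (500 trials per setting, 50 per arm, dropout 26–27% v 49–51%, slope for change −0.09 to −0.50) compared the planned model with the interaction model. The shift was −0.16 and −0.23 points for hazard ratios of 1.35 and 1.65 per SD, −0.13 with a flatter slope change (−0.17 to −0.40), +0.28 when milder subjects left more often, and 0.00 with no dependence. Monte Carlo error was 0.02–0.03.

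**6. Scale.** In 400 trials of 50 per arm under D, the SD of the Week 24 estimate was 2.28 without the term and 2.29 with it. In the second simulation it was 2.04–2.25 and 2.04–2.26. So 0.13 / 2.1 = 6% of a standard error, 0.33 / 2.28 = 14.5%, and 0.75 / 2.28 = 33%. For a two-sided 80% interval, coverage is Φ(1.2816 − d) − Φ(−1.2816 − d), where d is bias divided by SE. It is 79.9% at d = 0.06, 79.5% at d = 0.145 and 77.6% at d = 0.33.

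**The case against.** A main-effect baseline covariate is a legitimate specification, and every input that generates the bias is assumed. Protocol 3.2 (Efficacy Measures) ties the expected excess of quetiapine XR discontinuation to tolerability, not to baseline severity. Entry at MADRS 25 or above narrows the baseline range. Even the sign is unknown. Only MADRS was simulated, and nothing suggests that side-effect dropout tracks baseline SDMT or TMT-Part B. The protocol's own MADRS endpoints are mostly handled in other ways: sustained remission and response use non-responder imputation with Mantel-Haenszel, and the insomnia comparison is descriptive. At 6 to 15% of a standard error, an 80% interval loses at most half a percentage point of coverage.

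All of that stands as an argument about priority. It does not make the single slope the better choice, because the interaction removed the bias in every setting at no visible cost.

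The per-visit ANCOVA for MADRS, HAM-A and MADRS-6 does let the baseline slope differ by visit. It rests on LOCF (plus BOCF for MADRS), so it covers the gap only partly, and only for those three scores.

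A reader might infer that the estimate is biased whenever dropout depends on baseline severity. Settings A and C contradict that. A might-be-universal reading, that every scale is affected, is also unsupported: CGI-S, PGI-S and HVLT-R do not use this model.

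**Conclusion.** The point holds as a conditional and modest one. The MMRM omits the baseline-by-time term, and it is reused for the ten sets of scores listed. Bias at Week 24 needs two things together: a baseline slope that changes over visits, and dropout related to baseline that leaves the arms' remaining subjects with different baselines. The assumed 50% against about 25% discontinuation makes the second plausible; the documents do not establish either.

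For MADRS, on assumed inputs, the size is about 0.13 to 0.33 points in central settings and up to about 0.75 if the dependence differs by arm, against a standard error of 2.1 to 2.3. The much larger figure of 2.85 needs an extreme combination and should not be quoted as an expectation. Sizes for the other scales are unknown.

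The main simulation left out the insomnia-status term and gave every subject a Week 2 visit. Neither simulation reported on Kenward-Roger degrees of freedom or the fallback covariance structures.

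Nothing here bears on the primary log-rank test. The affected results are secondary or exploratory estimates without multiplicity adjustment, and the bias alone is unlikely to reverse a conclusion.

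**What to change.** In SAP 5.3.1.2, add the baseline-score-by-time interaction to the MMRM, and state that it carries over, with the relevant baseline score, to HAM-A, QLDS, PROMIS-SD, PROMIS-SRI, SMDDS, SDMT, TMT-Part B, MADRS-6, MADRS-WOSI and the CSD-M parameters. Specify that LS means are estimated at the overall mean baseline. With no treatment-by-baseline term, that choice sets the level of the LS means and not the difference between arms.

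The cost is one fewer parameter than there are post-baseline visits: five for MADRS (six visits), three for HAM-A (four visits), two for SDMT and TMT-Part B (three visits). At 50 per arm the simulated MADRS standard error was 2.28 without the term and 2.29 with it. CGI-S, PGI-S and HVLT-R need no change on this account. Priority is minor.

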1.1. Trial Objectives

Objectives	Endpoints
Primary	

 To assess, in subjects with major depressive disorder (MDD) who have had an inadequate response to current antidepressant therapy with a selective serotonin reuptake inhibitor (SSRI) or serotonin-norepinephrine reuptake inhibitor (SNRI), the efficacy of flexibly dosed JNJ-42847922 (20 mg or 40 mg) compared to flexibly dosed quetiapine extended-release (XR) (150 mg or 300 mg) as adjunctive therapy to an antidepressant drug in delaying time to all-cause discontinuation of study drug over a 6-month (24-week) treatment period. 	
 Time to all-cause discontinuation of study drug.
Secondary	

 To assess the efficacy of JNJ-42847922 compared to quetiapine XR in the adjunctive treatment of MDD based on: 
 Achieving and sustaining remission of depressive symptoms Achieving and sustaining response of depressive symptoms Improving depressive symptoms in subjects with significant insomnia versus those without significant insomnia 	
 The proportion of subjects achieving (at Week 12) and sustaining remission at Weeks 18 and 24. Remission is defined as Montgomery-Asberg Depression Rating Scale (MADRS) total score ≤ 12. The proportion of subjects achieving (at Week 12) and sustaining response at Weeks 18 and 24. Response is defined as $\geq 50\%$ improvement from baseline MADRS total score. Change from baseline to Weeks 12, 18, and 24 in the MADRS total score in subjects with significant insomnia (baseline Insomnia Severity Index [ISI] score ≥ 15) versus those without significant insomnia (baseline ISI

Objectives	Endpoints
	score <15).

 - Improving anxiety symptoms 	
 - Change from baseline to Weeks 12, 18, and 24 in the 14-item Hamilton Anxiety Rating Scale (HAM-A) total score.

 • To assess the effect of JNJ-42847922 compared to quetiapine XR as adjunctive therapy for MDD on metabolic parameters during long-term (6 months) treatment, including: 	

 - Weight 	
 • The proportion of subjects with weight gain $\geq 7\%$ of baseline body weight at end-of-study assessment.

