5. EFFICACY

All efficacy analyses will be based on the full analysis set.

The efficacy variables for this study are listed in Table 4.

Table 4: Efficacy Variables

Efficacy Variable		Endpoint
Time to all-cause discontinuation of study drug	
 Time to all-cause discontinuation of study drug 	Primary
MADRS	
 Change from baseline to Weeks 2, 4, 6, 12, 18, and 24 in the MADRS total score The proportion of subjects achieving (at Week 12) and sustaining remission at Weeks 18 and 24. Remission is defined as MADRS total score ≤ 12. The proportion of subjects achieving (at Week 12) and sustaining response at Weeks 18 and 24. Response is defined as $\geq 50\%$ improvement from baseline MADRS total score. 	Secondary Secondary Secondary

Efficacy Variable		Endpoint
	
 Change from baseline to Weeks 12, 18, and 24 in the MADRS total score in subjects with baseline ISI score ≥ 15 versus subjects with baseline ISI score < 15 	Secondary
	
 Change from baseline to Weeks 2, 4, 6, 12, 18, and 24 in the MADRS-6 total score 	Secondary
	
 Change from baseline to Weeks 2, 4, 6, 12, 18, and 24 in the MADRS-WOSI total score 	Exploratory
HAM-A	
 Change from baseline to Weeks 6, 12, 18, and 24 in the HAM-A total score 	Secondary
CGI-S	
 Change from baseline to Weeks 2, 4, 6, 12, 18 and 24 	Secondary
PGI-S	
 Change from baseline to Weeks 2, 3, 6, 12, 18 and 24 	Secondary
QLDS	
 Change from baseline to Weeks 2, 4, 6, 12, 18 and 24 	Secondary
PROMIS-SD	
 Change from baseline to Weeks 2, 6, 12, 18 and 24 	Secondary
PROMIS-SRI	
 Change from baseline to Weeks 2, 6, 12, 18 and 24 	Secondary
SMDDS	
 Change from baseline to Weeks 2, 4, 6, 12, 18 and 24 	Secondary
SDMT	
 Change from baseline to Weeks 6, 12, and 24 	Secondary
TMT-Part B	
 Change from baseline to Weeks 6, 12, and 24 	Secondary
HVLT-R	
 Change from baseline to Weeks 6, 12, and 24 	Secondary

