5.2.3.1. Subgroup Analyses

Descriptive statistics (number of discontinuations, number of censored subjects, median, 25th and 75th percentile, if estimable) will be provided for the primary efficacy endpoint (time to all-cause discontinuation of study drug) by the subgroups identified in Section 2.6. Subgroup analysis will be performed using the Cox proportional hazards model. The model will include terms for treatment, subgroup and treatment-by-subgroup. One subgroup at a time will be included in the model. A forest plot with the corresponding hazard ratios and 80% CI will be presented for the subgroups. If there are insufficient numbers in the subgroups to draw meaningful conclusions, the subgroup analysis will not be performed. The Kaplan-Meier plots will be provided for the subgroups with baseline ISI ≥ 15 and baseline ISI < 15 .

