As a sensitivity analysis, the change in MADRS total score from baseline to each postbaseline time point in the double-blind phase will be analyzed using an ANCOVA model, using LOCF and BOCF data. The ANCOVA model will include factors for treatment, baseline insomnia status (present/absent), and baseline MADRS total score as a continuous covariate. A 80% CI for the difference in LS Means will be calculated based on the contrast test statistic.

The last postbaseline observation during the double-blind phase will be carried forward as the “End Point (DB)” for that phase. Besides the end point assessment, the LOCF values will be created for intermediate postbaseline time points as well. These imputed time points will be labeled ‘WEEK X LOCF’.

For example, if a subject has a visit on Day 125 for the Week 18 visit and then a final visit on Day 130, the visit on Day 125 will be slotted to “Week 18” and “Week 18 LOCF” because Day 125 is closer to the target Day 126 than Day 130. The Day 130 visit will be used as “Week 24 LOCF” and “End Point (DB)”.

For subjects who discontinue treatment early, impute the missing MADRS scores post-discontinuation as the baseline value, and label as “Week xx BOCF” or “End Point (DB) BOCF”.

As a secondary analysis, age and gender will be added to the ANCOVA model.

SUBGROUP ANALYSIS

Baseline ISI Score

The ISI has 7 questions, each rated on a 5-point Likert scale ranging from 0 to 4. The total score is the sum of each individual item and can range from 0 to 28 (28 = most severe insomnia).

Subjects will be dichotomized based on their baseline ISI score (≥ 15 versus < 15) to evaluate whether there are differences in these subgroups (i.e., evaluating change from baseline to each postbaseline time point in the MADRS total score in subjects with ISI score ≥ 15 versus subjects

with ISI score <15). Descriptive statistics of the change from baseline to each postbaseline time point in the MADRS total score will be presented by treatment group for these subgroups.

Mode Dose

Descriptive statistics of the change from baseline to each postbaseline time point in the MADRS total score will be presented by treatment group and mode dose as defined in Section 4.4.

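### The secondary endpoint of MADRS change by baseline insomnia stratum gets descriptive statistics only: SAP 5.3.1.2 specifies no within-stratum treatment difference and no confidence interval.

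*SAP*

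**What the plan says.** - **Objective and endpoint.** SAP 1.1 sets the secondary objective "To assess the efficacy of JNJ-42847922 compared to quetiapine XR in the adjunctive treatment of MDD based on" a list that includes "Improving depressive symptoms in subjects with significant insomnia versus those without significant insomnia". SAP Table 4 (Section 5) gives this its own row, ranked secondary and separate from overall MADRS change: "Change from baseline to Weeks 12, 18, and 24 in the MADRS total score in subjects with baseline ISI score" at or above 15 versus below 15.
- **Design.** Protocol 3.2 explains that randomisation is stratified by ISI so that improvement with and without significant insomnia can be examined. SAP 2.6 designates the IWRS stratum as baseline insomnia status for the analyses.
- **General rule.** SAP 5.1.1: "For all other efficacy endpoints, no multiplicity adjustment will be done and point estimates and confidence intervals will be presented". Protocol 11.3 promises nominal p-values for the same endpoints.
- **Planned analysis.** SAP 5.3.1.2, under Baseline ISI Score, is limited to descriptive summaries: "change from baseline to each postbaseline time point in the MADRS total score will be presented by treatment group for these subgroups".
- **MADRS models in the same section.** After time and treatment, the MMRM has "baseline insomnia status (present/absent), and treatment-by-time interaction as factors", with baseline MADRS as covariate. For the sensitivity analysis, "The ANCOVA model will include factors for treatment, baseline insomnia status (present/absent), and baseline MADRS total score as a continuous covariate".
- **Primary endpoint, for comparison.** The Cox subgroup analysis in SAP 5.2.3.1 states: "The model will include terms for treatment, subgroup and treatment-by-subgroup". It reports subgroup hazard ratios with 80% CIs.

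**The concern.** The SAP poses a comparative question in each insomnia stratum and then specifies no statistic that answers it. Arm means by stratum are not a treatment difference, and they come without an interval.

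If nothing changes, this secondary endpoint is reported without a pre-specified, baseline-adjusted estimate of JNJ-42847922 against quetiapine XR in subjects with and without significant insomnia. Readers would build their own contrasts from N, mean and SD. Those would be post hoc and unadjusted for baseline MADRS, and bare means in small cells are easily over-read. The SAP already uses the suitable approach, a treatment-by-subgroup model with 80% CIs, for time to discontinuation.

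**Working it through.** **1. Is the estimate specified anywhere?** The places in the SAP that bear on a MADRS or ISI analysis are Sections 2.6, 5 (Table 4), 5.1.1, 5.1.2, 5.2.3.1 and 5.3.1.2. None gives a within-stratum treatment difference for MADRS, an interval for one, or a treatment-by-insomnia contrast. The SAP's lists of descriptive statistics (Sections 4.1 and 4.4) are N, mean, SD, median and range, with no interval.

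**2. Can the planned models supply it?** In the MMRM the only interaction is treatment-by-time, and the ANCOVA has none. With insomnia as a main effect, each returns one treatment difference per visit, common to both strata. Suppose the true Week 24 differences were -4 (ISI at or above 15) and 0 (below 15), both assumed. Stratum weighting gives:

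- equal strata: 0.5 × (-4) + 0.5 × 0 = -2.0
- 30/70 split: 0.3 × (-4) + 0.7 × 0 = -1.2

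Simulated fits of the planned MMRM agree: -2.05 and -2.07 on average with equal strata (SD 8 and 12), and -1.25 with 30/70.

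**3. Retention, from the plan's sizing assumptions.** SAP 1.4 has 50 subjects per arm, 50% discontinuation on quetiapine XR and a hazard ratio of 0.415. JNJ-42847922 discontinuation is then 1 - 0.5^0.415 = 25%, giving 50 × 0.50 + 50 × 0.25 = 37.5 events. Power is Φ(√(37.5/4) × |ln 0.415| - 1.2816) = Φ(1.41) = 92.1%, which reproduces the stated 92%. With constant hazards (assumed), retention to week w is 0.5^(w/24) on quetiapine XR and 0.75^(w/24) on JNJ-42847922.

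**4. Precision of the missing estimates.** Unadjusted 80% half-width = 1.2816 × SD × √(1/n_q + 1/n_j). The between-stratum contrast uses the root sum of squares of the two stratum standard errors. The documents give no SD of MADRS change, so 8 to 12 is assumed. Equal strata (25 per arm) are also assumed.

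| Week | n per stratum (quetiapine XR / JNJ) | Half-width per stratum | Half-width of contrast |
|---|---|---|---|
| 12 | 17.7 / 21.7 | 3.3–4.9 | 4.6–7.0 |
| 18 | 14.9 / 20.1 | 3.5–5.3 | 5.0–7.4 |
| 24 | 12.5 / 18.8 | 3.7–5.6 | 5.3–7.9 |

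Example, Week 24, SD 8: 1.2816 × 8 × √(1/12.5 + 1/18.75) = 3.7; the contrast is 3.74 × √2 = 5.3.

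- With t quantiles, the Week 24 values are 3.8–5.7 and 5.4–8.0.
- With a 30/70 split, the Week 24 values are 4.8–7.2 (smaller stratum), 3.2–4.7 (larger stratum) and 5.8–8.7 (contrast).
- Overall at Week 24 (25 against 37.5 subjects), the half-width is 2.6–4.0.

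**5. Is the fuller model feasible?** Simulation settings: 100 subjects, 6 visits, REML with unstructured covariance, correlation 0.5, dropout depending on the last observed MADRS change and calibrated to 50%/25%, and 500 trials in each of three settings. A model with all insomnia interactions converged in 1,500 of 1,500 trials. Its 80% intervals covered the stratum and contrast values in 77–82% of trials at Weeks 12, 18 and 24. Mean Week 24 half-widths (stratum / contrast) with equal strata were 3.3 / 4.7 (SD 8) and 5.0 / 7.0 (SD 12). With 30/70 strata and SD 8 they were 4.3 (smaller), 2.8 (larger) and 5.1 (contrast). The degrees of freedom were retained subjects minus parameters, not Kenward-Roger. The SDs, correlation, effects and dropout slopes are all assumed.

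**The case against.** **SAP 5.1.1 is a general sentence.** It names no stratum and no treatment difference, and the SAP does not follow it everywhere: HVLT-R (5.3.13.2) is also descriptive only. This stands as a description. It means that the mismatch is wider than this endpoint, and it does not supply the missing interval. HVLT-R did not determine the stratification; insomnia status did.

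**The literal wording compares insomnia with no insomnia**, which points to the between-stratum contrast more than to the within-stratum drug difference, and no formal hypothesis is stated for this endpoint. That is a fair reading. The parent objective is nevertheless a comparison with quetiapine XR, and neither quantity is specified. The fix reports both.

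**Descriptive reporting is a permissible choice** in an exploratory Phase 2 trial, since Protocol 11.3 leaves secondary methods to the SAP, and an unadjusted difference can be derived from the table. The SAP may choose this, but the choice does not sit with its own Section 5.1.1, and a difference derived later is not pre-specified.

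**The added output is imprecise and the model is larger.** This stands. The interactions add 11 fixed-effect parameters (1 + 5 + 5), for 24 treatment-stratum-visit means. With a 30/70 split the smallest Week 24 cell holds about 15 × 0.5 = 7.5 quetiapine XR subjects. Imprecision argues for showing the interval and against treating the result as a test.

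**The averaging result follows by construction.** True. It is there only to show that the common difference cannot stand in for the stratum estimates.

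**Conclusion.** The concern holds. It rests on the text: a named comparative secondary endpoint, tied to the stratification factor, has no treatment estimate or interval specified, and the planned models cannot produce one by stratum. The numbers show scale only and depend on the assumed SDs, constant hazards and stratum split. On those assumptions the intervals would be about 1.4 times (√2) as wide per stratum as overall, and twice as wide for the contrast. They can show a stratum estimate with its uncertainty and little more. The change should be made, but nothing here touches the primary analysis.

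**What to change.** Keep the descriptive table and add the following to SAP 5.3.1.2, before unblinding:

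> For this endpoint the MADRS MMRM will also be fitted with treatment-by-insomnia, insomnia-by-time and treatment-by-insomnia-by-time terms, using the IWRS stratum (Section 2.6) and the same covariance fallback order. The LS-mean difference (JNJ-42847922 minus quetiapine XR) with 80% CI will be presented in each ISI stratum at Weeks 12, 18 and 24. The between-stratum contrast with 80% CI from the same model will be given as a supporting estimate. These results are exploratory.

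The cost is one further fit of an extended version of a planned model, plus the SAP wording. Made after unblinding, it would be post hoc. Without a placebo arm the results are relative to quetiapine XR only, so a null difference in a stratum would not show absence of effect. Fitting a separate MMRM in each stratum would also give the within-stratum differences, but it would estimate the unstructured covariance from about half the subjects.
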